5.2.4.3 To Initiate SOC Treatment

If the subject is randomized to the SOC treatment and they use locally sourced SOC, they will receive the following SOC anticoagulant treatment according to the clinical site's usual treatment practice (alone or in combination):

- LMWH (alone or with VKA)
- UFH (alone or with VKA)
- VKA (alone or with LMWH or UFH)

For subjects who do not receive VKA treatment prior to randomization and are randomized to SOC with VKA, VKA treatment may be started on the day of randomization (Day 1).

It is per Investigator's discretion based on his/her local practice and on the subject's underlying cardiac disease to consider if heparin bridging is necessary post-randomization until an INR between 2.0 and 3.0 is reached. Heparin bridging will be provided by the Investigator.

If centrally sourced SOC treatment is required from the Sponsor, the subject will be treated as follows:

- For subjects randomized to enoxaparin: Neonates or children receiving either once- or twice-daily therapeutic enoxaparin should be monitored as per local practice.
- For subjects randomized to warfarin, it is recommended that the dose should be titrated to achieve a target INR of 2.0 to 3.0. It is per Investigator's discretion based on his/her local practice and on the subject's underlying cardiac disease to consider if heparin bridging is necessary during this period. Visits will be at the discretion of the Investigator and captured as unscheduled visits for data collection. Adjustment of the maintenance dose of VKA will be dependent on INR monitoring as follows:
 - INR 2.0 to 3.0, no change in dose
 - INR 1.1 to 1.4, increase dose by 20%
 - INR 1.5 to 1.9, increase dose by 10%
 - INR 3.1 to 3.5, decrease dose by 10%

INR >3.5, hold VKA until INR is <3.5, then decrease dose by 20% when restarted.

To initiate SOC post screening, it is recommended to test infants and children every 4 weeks once a stable dose of VKA has been achieved. However, depending on the site's clinical practice and PI's discretion, the subjects can be tested at the physician's discretion and/or according to local practice. More frequent INR testing is recommended in infants and children receiving VKA with any change in diet or medication or when an illness occurs. An unscheduled visit will need

to be performed to document the discretionary INR measurement and potential VKA dosage change as an unscheduled visit day.

For subjects on LMWH or UFH, periodic assessment of therapeutic level is recommended. The most widely used laboratory assay for monitoring UFH or LMWH therapy is the aPTT and anti-FXa activity. **All testing for therapeutic monitoring after randomization will be conducted locally**.

Guidance on dosing and dispensing is provided in Appendix 17.2.

5.2.5. Storage

Edoxaban tablets and granules for oral suspension must be stored at 20° to 25° C (68° to 77° F) with excursions permitted to 15° to 30° C (59° to 86° F).

SOC treatments must be stored as per labeled storage conditions.

All drug supplies must be stored in a secure, limited access storage area under the recommended storage conditions. If storage conditions go outside of allowable excursions, Sponsor/Contract Research Organization (CRO) must be contacted. The excursions will be discussed with the Sponsor and CRO to determine what action is necessary.

Storage temperatures must be recorded using devices such as a maximum/minimum thermometer. Temperature measurements will be recorded on a temperature log excluding weekends and holidays.

5.2.6. Drug Accountability

5.2.6.1. Edoxaban

Edoxaban will be provided by the Sponsor. When a drug shipment is received, the Investigator or designee will confirm the amount and condition of the drug and confirm the appropriate local language in the label, drug expiration date, and temperature monitor readings. The Investigator or designee will also sign the Receipt of Shipment Form provided and the form should be returned as instructed on the form. The original form will be retained at the clinical site. In addition, the Investigator or designee shall contact the Sponsor as soon as possible if there is a problem with the shipment and quarantine the shipment until the resolution is obtained from the Sponsor.

At the end of the study, or as directed, all drug products, including unused, partially used, or empty containers, will be destroyed, after full accountability. If drug destruction occurs at the clinical site, this must be approved in writing by the Sponsor and the Sponsor has received copies of the clinical site's drug handling and disposition standard operating procedures (SOPs).

For Sponsor provided drug, dosage form (ie, tablets and granule bottles) clinical site level accountability documentation is required as part of the disposition records of study drug. The dosage form site level accountability documentation should be appended to the Certificate of Destruction, if available.

The study drug will only be returned to a designee as instructed by the Sponsor if the clinical site is unable to perform the products destruction. Study drug will be returned only after the study monitor has completed a final inventory to verify the quantity to be returned. The

Proprietary and Confidential Page 62 return/destruction of products must be documented. At the end of the study, a final product reconciliation statement must be completed by the Investigator/designee and provided to the Sponsor.

Dosage form (ie, tablets and granule bottles) clinical site level accountability documentation is to be included with each drug supply return shipment (or other returning facility, such as another depot). This is required as part of the receiving records for return shipments.

All inventory forms must be made available for inspection by a Sponsor-authorized representative or designee and regulatory agency inspectors. The Investigator is responsible for the accountability of all used and unused study supplies at the clinical site.

5.2.6.2. Standard of Care

For both locally sourced SOC and Sponsor-provided SOC, a Drug Accountability Record will be used for the products. It may either be provided by the Sponsor or Sponsor representative, or the site may use a Sponsor approved form. The record must be kept current and must contain the dates and quantities of drug received from the central or local supply (for Sponsor provided therapy), subjects for whom the products was dispensed (identification number and/or initials or supply number as applicable), the date and quantity of study drug dispensed and remaining, if from individual subject drug units, as well as the initials of the dispenser. All unused drug and containers whether provided by the Sponsor or provided locally, must be brought back to the clinical site for accountability to support appropriate dosing instructions to the subject.

At the end of the study, or as directed, all drug products, including unused, partially used, or empty containers, will be destroyed, after full accountability. If drug destruction occurs at the clinical site, this must be approved in writing by the Sponsor and the Sponsor has received copies of the clinical site's drug handling and disposition SOPs). Locally sourced SOC should be destroyed at the clinical site.

For Sponsor-provided and locally supplied drug, dosage form (ie, tablets and syringes) site level accountability documentation is required as part of the disposition records of study drug. The dosage form site level accountability documentation should be appended to the Certificate of Destruction, if available.

The study drug will only be returned to a designee as instructed by the Sponsor if the clinical site is unable to perform the products destruction. Study drug will be returned only after the study monitor has completed a final inventory to verify the quantity to be returned. The return/destruction of products must be documented. At the end of the study, a final product reconciliation statement must be completed by the Investigator/designee and provided to the Sponsor.

Dosage form (ie, tablet, granule bottles, and syringes) site level accountability documentation is to be included with each drug supply return shipment (or other returning facility, such as another depot). This is required as part of the receiving records for return shipments.

All inventory forms must be made available for inspection by a Sponsor-authorized representative or designee and regulatory agency inspectors. The Investigator is responsible for the accountability of all used and unused study supplies at the clinical site.

5.3. Dose Interruptions and Reductions

If a subject's treatment with study drug must be interrupted for medical or surgical reasons (eg, hospital admission for an invasive procedure, a major medical condition, surgery, thrombocytopenia due to cytotoxic medication, or dental work); use of a prohibited concomitant medication; or other reasons (eg, temporary situation that prevents subject adherence with the study drug administration schedule, etc), the subject's study drug should be resumed as early as the situation allows. Edoxaban should be discontinued for 24 hours prior to the initiation of the procedures.

Subjects should be encouraged to restart study drug after an interruption except when absolutely contraindicated. The duration of study drug interruption can vary depending upon the individual circumstances, and study drug may be resumed regardless of the duration of time that it had been interrupted. Any subject who temporarily interrupts study drug more than 3 days will have the reason recorded in the electronic case report form (eCRF).

Any study drug interruption due to an adverse event should be reported on the Adverse Event eCRF, even if it is less than 3 days. A patient may have multiple interruptions of treatment throughout their study participation.

5.3.1. Edoxaban Dose Reduction

During the treatment period, a subject may reduce the dose of edoxaban for any of the following reasons:

• eGFR is 30-50% of normal for age and size (permanent dose reduction) (Appendix 17.9)

NOTE: If the repeat measurement confirms the decrease, the edoxaban dose will be reduced permanently. This dose reduction will be permanent even if the subject experiences an improvement in the eGFR during the course of the study.

- Subject is receiving concomitant treatment with P-gp inhibitors (temporary dose reduction)
- Body Weight:

For subjects 12 to <18 years old with body weight $<5^{th}$ percentile of subject's age (see Appendix 17.11), edoxaban doses will be permanently changed.

For subjects 12 to <18 years old with body weight ≥ 60 kg, will receive edoxaban 60 mg. However, if the body weight is $\geq 30 - \langle 60 \rangle$ kg, edoxaban dose would be 45 mg daily. If the patient body weight $\geq 60 \rangle$ kg, then edoxaban dose would be escalated to 60 mg daily.

For subjects <12 years old: Doses will be provided by mg/kg or a dose may be suggested, subsequent to exposure modeling, based on an age range (see Table 5.1).

For subjects receiving P-gp inhibitors during the study treatment period, the dose of edoxaban will only be reduced during the administration of the concomitant P-gp inhibitor. Subjects

experiencing eGFR or body weight reduction will maintain their reduced edoxaban dose for the duration of the study.

5.4. Method of Assessing Treatment Compliance

Dosing compliance for subjects in the edoxaban treatment arm will be assessed by means of tablet/bottle counts remaining and/or drug packaging/bottles returned. All drug packaging will be returned at each subject visit and will be accountable including bottles with dilutions made for dosing. Administration of the study drug will be recorded in the case report form (CRF)/eCRF/Drug Accountability Record. As necessary, include method of compliance calculation based on the returned number of tablets/bottles. If zero tablets/bottles returned, ask subject whether any were disposed or thrown away, rather than taken orally.

Subjects in the SOC (VKA) treatment arm will be monitored for compliance by measuring INR levels. Subjects in the SOC (UFH, LMWH) treatment arm will be monitored for compliance by measuring anti-FXa levels or aPTT. Compliance should be assessed routinely by the Investigator to ensure the adequate doses are taken (Table 17.1). Monitoring of heparin based treatment or VKA will be performed locally.

5.5. Prior and Concomitant Medications

Medications that the subject has taken within 30 days before screening will be recorded. In addition, anticoagulant and antiplatelet therapy will be recorded up to 3 months prior to randomization.

The following drugs and devices (see Appendix 17.5) CANNOT be used during the entire study treatment period and their unavoidable use would require study drug therapy interruption unless specifically indicated for study drug discontinuation:

- Anticoagulants, other than the assigned study drugs, by any route study drug should be discontinued
- Single or dual antiplatelet therapy with any antiplatelet agent is prohibited except for low dose aspirin defined as 1 to 5 mg/kg/day with maximum of 100 mg/day. If a clinical indication for antiplatelet therapy (other than low dose aspirin) arises after randomization, study drug should be temporarily interrupted and use of any other anticoagulation therapy is permitted at the physician's discretion.
- Chronic use of oral or parenteral non-steroidal anti-inflammatory drugs (NSAIDs) including both cyclooxygenase-1 and cyclooxygenase-2 inhibitors other than aspirin for ≥4 days/week. Use of NSAIDs via other routes (eg, topical, inhaled, intranasal, intraocular, etc) are not restricted (see Appendix 17.5.5).

All P-gp inhibitors (please refer to Appendix 17.6.1 for a list of the most commonly used P-gp inhibitors) excluding amiodarone will require dose reduction of edoxaban.

The Investigator is encouraged to contact a study physician (telephone number will be provided per country, per region; please refer to Study Manual for an appropriate phone number) if further guidance is needed.

Information regarding concomitant medications will be collected with start date, stop date, drug name, dose, and dosing regimen for population PK analyses at Month 1.

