2.3.1. Primary Safety Endpoint

The primary safety endpoint is a combination of major bleeding events and CRNM bleeding events per ISTH definition, occurring during the Main Treatment Period: from the date of first dose of study drug to the Month 3 Visit, or to the date of last dose of study drug plus 3 days if study treatment is discontinued, whichever is earlier.

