2.3.2. Secondary Safety Endpoint(s)

The secondary safety endpoints are:

• All bleeding events occurring during the Main Treatment Period: from the date of first dose of study drug to the Month 3 Visit, or to the date of last dose of study drug plus 3 days if study treatment is discontinued, whichever is earlier.

- A combination of major and CRNM bleedings from the day after Month 3 Visit to the date of the last dose of study medication plus 30 days for subjects who participate in the Extension Period.
- All bleeding events from the day after the Month 3 Visit to the date of last dose of study medication plus 30 days for subjects who participate in the Extension Period.

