17.4. Contraindications for Standard of Care Therapy

Contraindications to warfarin (COUMADIN):

- Hypersensitivity to the active substance or to any of the excipients
- Hemorrhagic stroke
- Clinically significant bleeding
- Use within 72 hours of major surgery with risk of severe bleeding
- Use within 48 hours postpartum
- Pregnancy
- Drugs where interactions may lead to a significantly increased risk of bleeding

Contraindications to enoxaparin (LOVENOX):

- Hypersensitivity to either enoxaparin sodium, heparin or its derivatives including other LMWH
- Acute bacterial endocarditis
- Active major bleeding
- Conditions with a high risk of uncontrolled hemorrhage, including recent hemorrhagic stroke or thrombocytopenia in subjects with a positive in-vitro aggregation test in the presence of enoxaparin; active gastric or duodenal ulceration
- Subjects receiving heparin for treatment rather than prophylaxis

Note: Loco-regional anesthesia in elective surgical procedures is contraindicated.

Contraindications to UFH:

- History of heparin-induced thrombocytopenia (with or without thrombosis)
- Uncontrolled, active bleeding (except disseminated intravascular coagulation)
- Acute bacterial endocarditis
- When suitable, blood-coagulation tests (eg, the whole-blood clotting time, partial thromboplastin time, etc) cannot be performed at appropriate intervals
- Hypersensitivity to heparin
- Advanced renal or hepatic dysfunction
- Severe hypertension
- Major surgery involving the brain, spinal cord and eye.

17.5. Prohibited Concomitant Medications at Any Time during the Treatment Period with Edoxaban or SOC

The list here (in the protocol) is static and reflects the list at the time of the current version of the protocol. If there are changes to this list during the study, the changes will not be considered a protocol amendment and the list in this appendix will not be updated unless the protocol is being amended for other reasons as well.

Subjects on these drugs at the time of planned randomization will be excluded from the study. After randomization, use of these drugs will require a study drug permanent discontinuation unless advised otherwise in the Sections below. The Investigator is encouraged to contact the Medical Monitor for further guidance.

Sites will receive a contact card where the following numbers (24-hour Urgent Medical Contact) are provided:

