17.5.1. Antiplatelet Drugs

Use of any antiplatelet medication as single or dual agent antiplatelet therapy is prohibited while on study drug except for low dose aspirin defined as 1 to 5 mg/kg/day with maximum of 100 mg/day. If there is a clinical indication for single or dual agent antiplatelet therapy, the subject will need to be discontinued from the study treatment.

Examples of non-aspirin oral antiplatelet agents include the following:

- Thienopyridines: clopidogrel (Plavix®), ticlopidine (Ticlid®), prasugrel (Effient®)
- Dipyridamole: Persantine®, Aggrenox®
- Cilostazol (Pletal®)
- Pentoxifylline (Trental®)
- Sulfinpyrazone (Anturane®)
- Ticagrelor (Brillanta®)

IV antiplatelet agents include the following:

- Glycoprotein IIb/IIIa inhibitors: Abciximab (ReoProTM), Eptifibatide (Integrilin®),
- Tirofiban (Aggrastat®)
- P2Y12 Inhibitor: Cangrelor
- Dextran

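### Section 5.5 interrupts study drug and Appendix 17.5.1 discontinues it for the same new antiplatelet indication; for a subject who resumes, the choice decides where the bleeding window ends

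*Combined protocol and SAP*

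**What the plan says.** **Section 5.5.** The list of prohibited drugs opens with a default: "their unavoidable use would require study drug therapy interruption unless specifically indicated for study drug discontinuation". The first bullet, on anticoagulants other than the assigned drug, calls for discontinuation of study drug. The second, on antiplatelet agents, exempts low-dose aspirin. For any other antiplatelet indication arising after randomization it says "study drug should be temporarily interrupted and use of any other anticoagulation therapy is permitted at the" physician's discretion.

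**Appendix 17.5 and 17.5.1.** The opening of 17.5 sets the reverse default: "After randomization, use of these drugs will require a study drug permanent discontinuation unless advised otherwise in the Sections below". Section 17.5.1 exempts the same low-dose aspirin and then says "If there is a clinical indication for single or dual agent antiplatelet therapy, the subject will need to be discontinued from the study treatment".

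**Section 5.3, repeated in 5.6.7.1.** Reasons for interrupting include "use of a prohibited concomitant medication". No maximum length is set: "study drug may be resumed regardless of the duration of time that it had been interrupted".

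**Sections 2.3.1, 2.3.2 and 11.4.3.1.** The primary bleeding window opens at first dose and normally closes at the Month 3 Visit. The alternative end is given as "or to the date of last dose of study drug plus 3 days if study treatment is discontinued, whichever is earlier". The all-bleeding endpoint has the same limits. Its definition begins "All bleeding events occurring during the Main Treatment Period: from the date of first dose of study drug to the Month 3 Visit" and continues with the same cut-off.

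**The concern.** The trigger is the same in both places, down to the aspirin exception, but the actions are opposite. Two sites with the same clinical event could each follow the protocol and treat their subjects differently.

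The conflict reaches the primary endpoint because the window turns on whether treatment is discontinued. It has no cut-off for an interruption. For a subject who would resume, the section the site follows therefore decides whether a bleed from the fourth drug-free day onward counts. The exploratory on-treatment efficacy window in Section 11.4.1.2 has the same cut-off. The secondary efficacy endpoints do not: they run from randomization to the Month 3 Visit whatever happens to treatment.

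In the Extension Period the choice also decides participation. Sections 5.6 and 5.6.2 take a subject who discontinues treatment out of the study, whereas an interrupted subject may resume.

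**Working it through.** **1. Can the text be reconciled as it stands?**

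- The exception in the 5.5 opening, for drugs marked for discontinuation, does not help, because the antiplatelet bullet beneath it specifies interruption.
- The exception in the 17.5 opening, for sections that advise otherwise, does not help, because 17.5.1 repeats discontinuation.
- The defaults are opposite: 5.5 interrupts unless told otherwise, and 17.5 discontinues unless told otherwise.
- Within 5.5, a subject given another anticoagulant during the interruption meets both the bullet that permits it and the bullet that discontinues study drug for it.

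**2. What happens to the window?** Let the last dose be on Day d, followed by L drug-free days, with dosing resumed on Day d + L + 1.

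- Stopped under 17.5.1: the window ends on Day d + 3.
- Interrupted under 5.5 and resumed: it ends at the Month 3 Visit, assumed here to be Day 90.
- Off-drug days counted only under 5.5: L − 3. For assumed L = 7, 14 or 28 this is 4, 11 or 25 days.

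Illustration with assumed d = 30 and L = 14: the window ends on Day 33 or Day 90, a difference of 90 − 33 = 57 days (52 to 62 with the ±5-day visit window). Of the 57, Days 34–44 (11 days) are off drug under either section. Days 45–90 (46 days) follow resumption, when actual treatment also differs. For a last dose on Day 15, 45, 60 or 75, the total difference is 72, 42, 27 or 12 days.

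If the subject never resumes, the last dose is the same under both sections. Should that subject be classed as discontinued, both windows end on Day d + 3. The text does not say when an interruption becomes a discontinuation.

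**3. How large is the effect?** Section 11.6 assumes rates of 8.5% (edoxaban, n = 100) and 10.3% (SOC, n = 50). Its interval reproduces with an unpooled Wald formula:

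- SE = √(0.085 × 0.915/100 + 0.103 × 0.897/50) = 0.0512
- −1.8 ± 1.96 × 5.12 = −11.8 to 8.2 percentage points, width 20.1

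Expected events are 100 × 0.085 = 8.5 and 50 × 0.103 = 5.15. One subject's first qualifying bleed, counted or not, moves crude incidence by 1/100 = 1.0 point or 1/50 = 2.0 points. That is 1.0/20.1 = 5.0% or 2.0/20.1 = 10.0% of the interval width.

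For person-time, assume 1 to 5 affected subjects, each losing 57 days. The arm total changes by 57/9000 = 0.6% to 285/9000 = 3.2% on edoxaban, or 57/4500 = 1.3% to 285/4500 = 6.3% on SOC. The number affected is an assumption; the documents give none.

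**The case against.** - **The endpoint consequence is conditional.** A reader might infer that every affected subject has a different window under the two sections. The documents do not support that. The windows clearly differ only for a subject who resumes, or who is at least not later classed as discontinued. This stands.
- **Most of the extra days are not a labelling artefact.** In the illustration, 46 of 57 days follow resumption, when one subject is back on drug and the other is not. The remaining 11 are a gap of the kind that any interruption creates, such as surgery or dental work. This stands as to size. The contradictory instruction remains, and here it decides which window applies.
- **Section 5.3 might seem to settle the matter for interruption.** It does not. The sentence is generic, names no antiplatelet agent, and is compatible with other prohibited drugs.
- **The two 5.5 bullets might be read apart,** the first covering use alongside study drug and the second use during a gap. The text does not say so, and the list applies to the entire study treatment period.
- **Sites can ask.** Section 5.5 points to a study physician and 17.5 to the Medical Monitor. That is a route to advice, but it is not a rule and does not ensure the same answer everywhere.
- **The analysis is descriptive.** The study is unpowered, and the main model is a time-to-event Cox regression, so only a first qualifying bleed matters and the percentage-point figures describe crude incidence only. This stands.

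**Conclusion.** The contradiction is real and in current text, both between 5.5 and 17.5/17.5.1 and between two bullets of 5.5. It should be corrected.

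Its statistical effect is limited. For a subject who resumes, the primary and all-bleeding windows end at the Month 3 Visit under one section and at last dose plus 3 days under the other; for a subject who never resumes they may coincide. One event is worth 1.0 or 2.0 points of crude incidence. The day counts rest on the assumed last-dose day, interruption length and Day 90 visit.

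A reader might conclude that the primary result is compromised. The documents do not support that: Sections 5.6.1 and 6.4.3 keep subjects under observation to Month 3 after a stop of either kind, so the counting can be made uniform before lock. What cannot be recovered is any difference in treatment already given. Nor can it be said that the definition is missing altogether: Section 11.7 leaves definitions to a SAP, and no separate SAP text is included here. No view is taken on which clinical action is right.

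**What to change.** 1. Reconcile Section 5.5 (both bullets) with 17.5 and 17.5.1, and align the prohibited-medication wording in 5.3 and 5.6.7.1, so that all give one action. The clinical team must choose it.
2. Before database lock, define discontinuation for the last dose plus 3 days window from recorded dosing dates: a permanent stop with no later dose before the Month 3 Visit. Apply it identically in both arms, whatever label the site used. A definition tied to the reconciled clinical rule would be worse, because it could cut off on-drug bleeds in a subject who had already resumed.

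The cost is amendment wording and one SAP definition. No further analysis is needed, and no new data item appears necessary: Section 5.4 records administration of study drug, 5.6 records discontinuation, and 5.6.1 records the date of last treatment. The 5.4 sentence stands in its paragraph on the edoxaban arm, so confirm that SOC stop and restart dates are captured to the same standard.
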